5.3.2.2. Adverse events

Incomplete AE-related dates will be imputed as follows:

- If the AE onset date is missing completely, then the onset date will be replaced by the start of study treatment.
- If only the day part of the AE onset date is missing, but the month and year are equal to the start of study treatment, then the AE onset date will be replaced by the start of study treatment. For example, if the AE onset date is --/JAN/2015, and study treatment start date is 15/JAN/2015, then the imputed AE onset date will be 15/JAN/2015.
- If both the day and month of the AE onset date are missing but the onset year is equal to the start of study treatment, then the onset date will be replaced by the start of study treatment. For example, if AE onset date is --/---/2014, and study treatment start date is 19/NOV/2014, then the imputed AE onset date will be 19/NOV/2014.
- In all other cases the missing onset day or missing onset month will be replaced by 1.
- Incomplete stop date will be replaced by the last day of the month (if day is missing only), if not resulting in a date later than the date of patient's death. In the latter case the date of death will be used to impute the incomplete stop date.
- In all other cases the incomplete stop date will not be imputed. If stop date of AE is after the date of cut-off, outcome of AE is ongoing at cut-off.

5.3.2.3. Prior and concomitant medications

Incomplete prior/concomitant medication dates will be imputed as follows:

- If the medication date is missing completely, then the medication date will be replaced by the start of study treatment.
- If the day of medication date is missing, but the month and year are equal to the start of study treatment, then the medication date will be replaced by the start of study treatment. For example, if the medication start date is --/JAN/2015, and study treatment start date is 15/JAN/2015, then the imputed medication start date will be 15/JAN/2015.
- If both the day and month of medication start date are missing but the start year is equal to the start of study treatment, then the medication date will be replaced by the start of study treatment. For example, if the medication start date is --/---/2014, and study treatment start date is 19/NOV/2014, then the imputed medication start date will be 19/NOV/2014.
- In all other cases the missing medication day or missing medication month will be replaced by 1.

- Incomplete stop date will be replaced by the last day of the month (if day is missing only), if not resulting in a date later than the date of patient's death. In the latter case the date of death will be used to impute the incomplete stop date.
- In all other cases the incomplete medication stop date will not be imputed.

5.3.2.4. Exposure

No imputation will be done for first dose date. Date of last dose of study drug, if unknown or partially unknown, will be imputed as follows:

- If the last date of study drug is completely missing and there is no End of Treatment eCRF page and no death date, the patient should be considered to be ongoing and use the cut-off date for the analysis as the last dosing date
- If the last date of study drug is completely or partially missing and there is EITHER an End of Treatment eCRF page OR a death date available (within the cut-off date), then imputed last dose date is:
 - = 31DECYYYY, if only Year is available and Year < Year of min (EOT date, death date)
 - = Last day of the month, if both Year and Month are available and Year = Year of min (EOT date, death date) and Month < the month of min (EOT date, death date)
 - = min (EOT date, death date), for all other cases.

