5.2.7. Definition of on-treatment period

Safety endpoints will be summarized based on the on-treatment period unless otherwise specified.

On-treatment period is defined as the time from the first dose of study treatment through minimum (30 days + last dose of study treatment, start day of new anti-cancer drug therapy – 1 day).

Safety data collected outside the on-treatment period as described above will be listed and flagged in listings but will not be summarized.

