 YYYY = Year of min [max(PD date + 1, last dose of study treatment + 1), end date of new anti-cancer therapy], AND
 MMM = Month of min [max(PD date + 1 day, last dose of study treatment + 1 day), end date of new anti-cancer therapy]
THEN

imputed start date = min [max(PD date + 1 day, last dose of study treatment + 1 day), end date of new anti-cancer therapy];

ELSE IF

YYYY = Year of min [max(PD date + 1, last dose of study treatment + 1), end date of new anti-cancer therapy], AND

MMM > Month of min [max(PD date + 1 day, last dose of study treatment + 1 day), end date of new anti-cancer therapy]

THEN

imputed start date = 01 MMM YYYY;

ELSE IF

YYYY < Year of min [max(PD date + 1, last dose of study treatment + 1), end date of new anti-cancer therapy]

THEN

imputed start date = DAY (Last day of MMM) MMM YYYY;

ELSE IF

YYYY > Year of min [max(PD date + 1, last dose of study treatment + 1), end date of new anti-cancer therapy]

THEN

imputed start date = 01 MMM YYYY.

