6.6.2. Deaths

The frequency (number and percentage) of patients in the safety analysis set who died and who died within 30 days after last dose of study treatment as well as the reason for death, will be tabulated based on information from the ‘Notice of Death’ and ‘Survival Follow-Up’ eCRFs, by treatment arm.

- All deaths
- Deaths within 30 days after last dose of study treatment
- Reason for Death
 - Disease progression
 - Study treatment toxicity
 - AE not related to study treatment
 - Unknown
 - Other.

In addition, date and cause of death will be provided in individual patient data listing together with selected dosing information (study treatment received, date of first / last administration, dose) and will include the following information:

- AEs with fatal outcome (list preferred terms of AEs with outcome=Fatal, as well as AEs of Grade 5),
- Flag for death within 30 days of last dose of study treatment.

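### SAP 5.3.2.4 has no branch for a last-dose date with a known month in a year before end of treatment or death, so it imputes a date that the record rules out

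*SAP*

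**What the plan says.** SAP 5.3.2.4 (Exposure) sets this condition: "If the last date of study drug is completely or partially missing and there is EITHER an End of Treatment eCRF page OR a death". Either record must fall within the data cut-off. It then gives three branches, where the reference date is the earlier of EOT and death:

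1. "31DECYYYY, if only Year is available and Year < Year of min (EOT date, death date"): year only, earlier year, so 31 December of that year.
2. The last day of the recorded month, "if both Year and Month are available and Year = Year of min (EOT date, death date) and Month < the month of min" (again of EOT and death).
3. "min (EOT date, death date), for all other cases".

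SAP 5.3.3.4 handles an incomplete start date of new anti-cancer therapy in a similar way. Where month and year are known, it has a separate branch for "YYYY < Year of min [max(PD date + 1, last dose of study treatment + 1), end date of new anti-cancer therapy"], with the result "imputed start date = DAY (Last day of MMM) MMM YYYY".

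The last-dose date is used in several places. SAP 5.2.7 states: "On-treatment period is defined as the time from the first dose of study treatment through minimum (30 days + last dose of study treatment", or the day before new anti-cancer drug therapy if that comes first). SAP 6.6.2 tabulates "Deaths within 30 days after last dose of study treatment". SAP 6.5.3.1 and 6.5.3.2 use it for duration of exposure. SAP Appendix 1 (Table 16, step 2) uses it for the 90-day window for immune-related events.

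**The concern.** A last dose with a known month and an earlier year fails branch 1, because the month is available. It fails branch 2, because the years differ. Only the default is left, and the default returns a date in a different month and year from the one recorded. Nothing else in the section covers the case.

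The result is also inconsistent within the rule: a less complete record (year only) gives a date that agrees with the data, and a more complete record (month and year) does not. Since branch 2 respects a known month within the same year, and 5.3.3.4 covers the earlier-year case, this looks like an omission rather than a choice.

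The error runs in one direction: the last dose is always moved later. At stake are exposure duration and the safety classifications that depend on time since last dose.

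**Working it through.** The plan gives no figure to reproduce. The check applies the three branches literally to illustrative partial dates, which are assumptions and not trial data. It then repeats them with branch 2 widened to any recorded month that precedes the month of the reference date.

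| Recorded | Reference date | As written | Widened | Difference (days) |
|---|---|---|---|---|
| 2017 only | 20JAN2018 | 31DEC2017 | 31DEC2017 | 0 |
| DEC2017 | 20JAN2018 | 20JAN2018 | 31DEC2017 | 20 |
| NOV2017 | 20JAN2018 | 20JAN2018 | 30NOV2017 | 51 |
| OCT2017 | 15FEB2018 | 15FEB2018 | 31OCT2017 | 107 |
| JUN2017 | 20MAR2018 | 20MAR2018 | 30JUN2017 | 263 |
| JAN2018 | 20MAR2018 | 31JAN2018 | 31JAN2018 | 0 |
| MAR2018 | 20MAR2018 | 20MAR2018 | 20MAR2018 | 0 |

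The four earlier-year rows with a known month contradict the record as written. The year-only and same-year rows are handled properly and do not change.

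**Size of the date error.** For December 2016 with EOT on 20 January 2017, the imputed date is 20 January 2017. From 31 December that is 20 days; from 1 December it is 30 + 20 = 50 days. The error is therefore 20 to 50 days.

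**Exposure.** Duration is (last dose − first dose + 14)/7 weeks for avelumab and (last dose − first dose + 28)/7 for PLD. Either is overstated by 20/7 = 2.9 to 50/7 = 7.1 weeks in this example.

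**On-treatment period.** As written it ends on 20 January + 30 days = 19 February 2017, unless new anti-cancer drug therapy ends it sooner. From the true last dose it would end between 31 December 2016 (1 December + 30) and 30 January 2017 (31 December + 30).

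**30-day death flag.**
- December 2016, death on 25 January 2017, no earlier EOT date: the imputed gap is 0 days. The true gap is 25 days (from 31 December) to 30 + 25 = 55 days (from 1 December). It exceeds 30 days for any dose before 26 December. The widened rule gives 31 December and a gap of 25 days, so the flag stays set: the date now agrees with the record, but the flag remains uncertain.
- November 2017, death on 20 January 2018, no earlier EOT date: the imputed gap is 0 days and the flag is set. The true gap is 51 days (from 30 November) to 29 + 51 = 80 days (from 1 November), so the flag is certainly wrong. The widened rule gives 51 days and no flag.

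**Link to PFS.** Last dose + 1 enters the imputation of the new-therapy start date in SAP 5.3.3.4 only if that start date is itself incomplete. It matters only if last dose, not investigator-assessed progression, sets the maximum, and no earlier therapy end date sets the minimum. Since SAP 6.1.2.1 censors at the last adequate tumor assessment, an assessment or event must also fall between the two candidate dates.

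**The case against.** The best argument on the other side is that the case may never arise. Both drugs are infused at the site (Protocol 5.2.3), avelumab infusion times are recorded in source documents and CRFs (Protocol 5.2.3.3), drug accountability is kept per patient with dates (Protocol 5.3.2), and analyses use cleaned data (SAP 2). A missing day, a recorded month and a reference date in a later year must all coincide. This stands as a limit on the size of the problem. It does not show that the case cannot occur: SAP Tables 6 and 7 put the final analysis at 27 to 31 months, so the study crosses at least two year boundaries.

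Three stronger readings are tempting, and the documents do not support them.

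- A reader might infer that a death soon after the year boundary is always flagged as within 30 days. The rule takes the earlier of EOT and death. With EOT on 20 December 2016 and death on 25 January 2017, a December 2016 record is imputed as 20 December, the gap is 11 + 25 = 36 days, and no flag is set.
- A reader might infer that late adverse events and deaths are routinely labelled on-treatment. New anti-cancer drug therapy also ends the period (SAP 5.2.7), and an event is misclassified only if it falls in the added days. The date is wrong every time; the classification need not be.
- A reader might infer that the primary PFS analysis is biased. That needs the chain of conditions set out above.

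None of this gives a reason to keep the present wording.

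**Conclusion.** The rule is wrong as written for one pattern of partial date: month and year known, with the year earlier than that of the earlier of EOT and death. Each time the pattern occurs, the imputed date contradicts the record and exposure is overstated. Effects on the on-treatment period, the immune-related window and the death flag are possible but depend on the patient. With an EOT date shortly after the last dose the shift is limited. With no EOT date, the only limit is the time to death.

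This is a minor point. PFS could be touched only remotely. OS is not affected, because SAP 5.3.3.1 derives last contact from complete dates. The day counts rest on illustrative dates. The documents do not say how many last-dose dates were partial; the number affected is probably small and may be zero.

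**What to change.** Reword branch 2 as: the last day of the recorded month, if month and year are both known and either the year is earlier than the year of min(EOT date, death date), or the years are equal and the month is earlier. Leave branches 1 and 3 unchanged. The new result always precedes the reference date, and year-only and same-year cases are not altered.

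Protocol Section 9 states that the final analysis is complete. The sponsor should therefore also list any patients whose last-dose date was imputed across a year boundary, confirm what the program did, and correct their derived exposure and safety values.

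The cost is one clause in the SAP and the program, one data query and, only if patients are affected, a rerun of the tables concerned.

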5.3.3. Imputation rules for date of last contact and efficacy assessments

5.3.3.1. Date of last contact

The date of last contact will be derived for patients not known to have died at the analysis cut-off using the latest complete date among the following:

- All patient assessment dates (blood draws (laboratory, PK), vital signs, performance status, ECG, tumor assessments)
- Start and end dates of anti-cancer therapies administered after study treatment discontinuation
- AE start and end dates
- Last date of contact collected on the 'Survival Follow-up' eCRF (do not use date of survival follow-up assessment unless status is 'alive')
- Study drug start and end dates
- Randomization date
- Withdrawal of consent date
- Date of discontinuation on disposition eCRF pages (do not use if reason for discontinuation is lost to follow-up).

Only dates associated with actual examinations of the patient will be used in the derivation. Dates associated with a technical operation unrelated to patient status such as the date a blood sample was processed will not be used. Assessment dates after the cut-off date will not be applied to derive the last contact date.

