5. **Safety Follow-up:** All patient safety follow-up visits are scheduled monthly for 90 days after the last dose of study treatment (Day 30 \pm 3, Day 60 \pm 3, Day 90 \pm 3). Final visit is scheduled to occur at least 90 days, and no more than 93 days, after the last dose of study treatment. PK sample collection is only required at the first follow-up visit (Day 30).
6. **Follow-up for PFS and OS:** Patients without evidence of disease progression at the time of treatment discontinuation should remain on the study and continue to have tumor assessment radiological scans every 8 weeks until documented progressive disease. Patients who have discontinued study treatment due to progressive disease should be followed for survival every 12 weeks via telephone call until study end. Additionally, subsequent anti-cancer therapies, surgery, and date of initiation and discontinuation of each anti-cancer drug will be recorded in the CRF.
7. **Informed Consent:** Must be obtained prior to undergoing any study-specific procedures.
8. **Tumor History:** Includes collection of tumor history, prior antitumor regimen(s), including treatment duration and best response observed.
9. **Physical Examination:** Includes an examination of major body systems, and weight (height included at screening only). Abnormal findings identified prior to first dose of study treatment should be documented in medical history.
10. **Baseline Signs & Symptoms:** Patients will be asked about any signs and symptoms experienced within the 14 days prior to study enrollment. Baseline signs and symptoms will be recorded on the Medical History case report form (CRF) page.
11. **Vital Signs:** Blood pressure (BP) and pulse rate should be taken before any other assessments (eg, PK, laboratory blood draws) with the patient in the seated position after the patient has been sitting quietly for at least 5 minutes.
12. **ECOG Performance status:** Use Eastern Cooperative Oncology Group (ECOG) – see [Appendix 2](#).

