5. GENERAL METHODOLOGY AND CONVENTIONS

5.1. Hypotheses and Decision Rules

5.1.1. Hypotheses and sample size determination

The study is designed to test, in parallel, the following hypotheses:

$$H_{01}: HR_{OS(avelumab/PLD)} \geq 1, \text{ versus } H_{a1}: HR_{OS(avelumab/PLD)} < 1$$

$$H_{02}: HR_{OS(avelumab+PLD/PLD)} \geq 1, \text{ versus } H_{a2}: HR_{OS(avelumab+PLD/PLD)} < 1$$

$$H_{03}: HR_{PFS(avelumab/PLD)} \geq 1, \text{ versus } H_{a3}: HR_{PFS(avelumab/PLD)} < 1$$

$$H_{04}: HR_{PFS(avelumab+PLD/PLD)} \geq 1, \text{ versus } H_{a4}: HR_{PFS(avelumab+PLD/PLD)} < 1$$

where HR_{OS} represents the hazard ratio for OS in each of the experimental arms vs the control arm, and HR_{PFS} represents the hazard ratio for PFS by BICR assessment in each of the experimental arms vs the control arm.

The treatment effects on the primary PRO endpoint, time to deterioration (TTD), will also be tested.

$$H_{05}: HR_{TTD(avelumab/PLD)} \geq 1, \text{ versus } H_{a5}: HR_{TTD(avelumab/PLD)} < 1$$

[figure not shown]
$$H_{06}: HR_{TTD(avelumab+PLD/PLD)} \geq 1, \text{ versus } H_{a6}: HR_{TTD(avelumab+PLD/PLD)} < 1$$

where HR_{TTD} represents the hazard ratio for TTD in each of the experimental arms vs the control arm.

Approximately 550 patients will be randomized to the treatment arms using a 1:1:1 randomization, stratified by platinum-refractory or platinum-resistant status, number of prior regimens (1 vs 2 or 3), and bulky disease (defined as presence of a tumor ≥ 5 cm) vs not.

Overall type I-error will be maintained at or below 1-sided 0.025 by allocating 0.0115 alpha to each of the two OS comparisons and 0.001 to each of the two PFS comparisons. A gatekeeping procedure will be used to allow further testing of TTD for patients as described in Figure 1. The significance levels for each test will also take into account the group sequential nature of the design.

Figure 1 Testing Strategy

For each of the two OS comparisons, 196 OS events will be required to have at least 90% power to detect a hazard ratio of 0.6 using a 1-sided log-rank test at a significance level of 0.0115, and a 2-look group-sequential design with Lan-DeMets (O'Brien-Fleming) α -spending function to determine the efficacy boundary and a Gamma Family (-10) β -spending function to determine the non-binding futility boundary.

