5.2.1. Data handling after the cut-off date

Data after the cut-off date may not undergo the cleaning process and will not be displayed in any listings or used for summary statistics, statistical analyses or imputations.

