6.1. Primary Endpoints

6.1.1. Overall survival

6.1.1.1. Primary analysis

The following analyses will be based on the FAS using the strata assigned at randomization.

Overall survival (OS) is defined as the time from the date of randomization to the date of death due to any cause. Patients last known to be alive will be censored at date of last contact.

$$\text{OS (months)} = [\text{date of death or censoring} - \text{date of randomization} + 1] / 30.4375$$

The primary analysis of OS will compare the OS time between each of the experimental arms and the control arm, and will be performed using a 1-sided stratified log-rank test as described in Section 5.1.

The treatment effect, as measured by the hazard ratio, will be estimated using a Cox's Proportional Hazard model stratified by the randomization strata. Each stratum will define a separate baseline hazard function (using the 'STRATA' statement in SAS PROC PHREG), ie, for the i -th stratum the hazard function is expressed as: $h(i;t) = h(i,0;t) \exp(x\beta)$, where $h(i,0;t)$ defines the baseline hazard function for the i -th stratum and x defines the treatment arm (0 =control arm, 1 = experimental arm) and β is the unknown regression parameter.

Ties will be handled by replacing the proportional hazards model by the discrete logistic model (Ties=Discrete option in SAS PROC PHREG).

In order to account for the group sequential design in this study, the repeated CI (RCI) method (Jennison and Turnbull, 2000), will be used to construct the 2-sided RCIs for the hazard ratio at the interim and the final analyses of OS.

In addition, the unadjusted 95% CIs for the hazard ratio will also be reported at the interim and the final analyses for OS.

Kaplan-Meier estimates (product-limit estimates) will be presented by treatment arm together with a summary of associated statistics including the median OS time with 2-sided 95% CIs. In particular, the OS rate at 6, 12, 18, 24 and 30 months will be estimated with corresponding 2-sided 95% CIs. The CIs for the median will be calculated according to Brookmeyer and Crowley (1982) and the CIs for the survival function estimates at the time points defined above will be derived using the log-log transformation according to Kalbfleisch and Prentice (2011) (conftype=loglog default option in SAS Proc LIFETEST) with back transformation to a CI on the untransformed scale. The estimate of the standard error will be computed using Greenwood's formula.

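### OS censoring in SAP 5.3.3.1 discards proof of survival past the cut-off, so the 24-month Kaplan-Meier OS rate reads low in every arm if deaths in the same window are counted

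*SAP*

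**What the plan says.** The primary OS analysis (SAP 6.1.1.1) provides that "Patients last known to be alive will be censored at date of last contact". SAP 5.3.3.1 builds that date from visits, laboratory draws, scans, later therapies, adverse events and survival follow-up, and closes with "Assessment dates after the cut-off date will not be applied to derive the last contact date". SAP 5.2.1 adds that data after the cut-off "will not be displayed in any listings or used for summary statistics, statistical analyses or imputations". No provision moves a patient known to be alive after the cut-off up to the cut-off date, and no survival sweep at the cut-off is described.

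Under the schedule in force until the final analysis (Protocol, Schedule of Activities, footnote 6), patients who stopped treatment for progression "should be followed for survival every 12 weeks via telephone call until study end". Patients without progression had scans every 8 weeks.

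Among the outputs of the primary analysis, "the OS rate at 6, 12, 18, 24 and 30 months will be estimated". The same section plans a reverse Kaplan-Meier summary of follow-up. SAP Table 8 gives *Lost to follow-up* as the censoring reason when the last contact is more than 13 weeks before the cut-off.

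**The concern.** Take a patient last reached eight weeks before the cut-off. If she dies in those eight weeks and the site reports it before lock, she is an event in that interval. If she lives, and the next call proves it, she leaves the risk set at the earlier contact. Deaths in the window stay in the numerator while survivors are removed from the denominator, so the estimated hazard is too high and the Kaplan-Meier curve too low. The effect falls on later follow-up times, where patients are close to their cut-off.

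Several provisions point to deaths being selected by their own date. OS is defined by date of death. SAP 5.3.2.4 screens death dates against the cut-off. SAP section 2 sets the cut-off from an extract taken before lock and accepts that event counts may then change with cleaning. At stake are the reported OS rates and the follow-up summary for a primary endpoint.

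**Working it through.** **1. The plan's own figure.** SAP 5.1.1 says "196 OS events will be required to have at least 90% power to detect a hazard ratio of 0.6", at one-sided alpha 0.0115. Schoenfeld: events = 4(z_α + z_β)² / (ln HR)² = 4(2.273 + 1.282)² / (ln 0.6)² = 50.55 / 0.2609 ≈ 194, within 3% of 196. The exact two-look calculation at 131 and 196 events gives interim z = 2.8791 (stated −2.8791), final p = 0.0109 (stated < 0.011) and power 0.901. The design assumptions are therefore understood correctly.

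**2. Inputs.** From SAP 5.1.1: OS medians 12 and 20 months, PFS medians 3.5 and 5.8 months, 19 months of accrual, 12 months' minimum follow-up, and 550/3 ≈ 183 patients per arm. Month 31 is 19 + 12, and is the final-analysis time in SAP Table 6 under HR 0.6. True 24-month OS is 2^(−24/12) = 25.0% on PLD and 2^(−24/20) = 43.5% on experimental treatment.

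Assumptions not in the documents: accrual shape (t/19)^p with p = 1, 1.5 or 2; exponential times; no drop-out; contacts every 2 weeks (avelumab) or 4 weeks (PLD) until progression, then at days 30, 60 and 90, then every 12 weeks.

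**3. Lost time.** Over 3,000 simulated trials per scenario, the mean gap from last contact to cut-off among survivors is 5.0 to 5.9 weeks. With contact every 8 weeks after treatment it is 3.5 to 3.9 weeks, and every 4 weeks 1.9 to 2.0.

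**4. 24-month OS (%), cut-off at month 31, every death up to the cut-off counted.** Each cell shows the SAP rule / censoring at the cut-off.

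| p | PLD (true 25.0) | Experimental (true 43.5) | Arm difference |
|---|---|---|---|
| 1 | 22.9 / 25.0 | 41.5 / 43.5 | 18.6 / 18.5 |
| 1.5 | 22.0 / 25.0 | 40.4 / 43.4 | 18.4 / 18.4 |
| 2 | 20.9 / 25.0 | 39.4 / 43.5 | 18.5 / 18.5 |

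The SAP rule is 2.0 to 4.1 points low in each arm, and the arm difference does not move. With the cut-off at month 34 the shortfall is 1.2 to 2.7 points. The 12-month rate shifts by 0.2 points or less.

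**5. Dependence on the deaths counted.** Month 34, p = 1, by the share captured of deaths falling between last contact and cut-off:

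| Share captured | PLD | Experimental |
|---|---|---|
| 100% | 23.6 (−1.4) | 42.1 (−1.4) |
| 50% | 24.4 (−0.6) | 42.7 (−0.8) |
| 0% | 25.0 (0) | 43.6 (+0.1) |

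If deaths are learned only at scheduled calls before lock, the 24-month shortfall is about 1 point with a 4-week lock interval and about 2 points with 8 weeks or more. The rule proposed below removes it.

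**6. The test.** 6,000 trials, p = 1.5, month 31, single look at 0.0115, SAP rule against cut-off censoring:
- Null, equal PFS: rejection 0.0108 vs 0.0110.
- Null OS, longer PFS on experimental treatment: 0.0127 vs 0.0117. The simulation error of each is √(0.0115 × 0.9885 / 6000) ≈ 0.0014.
- HR 0.6: estimated HR 0.596 vs 0.599.

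**7. 30 months.** At month 31 at most 0.7 patients per arm remain at risk under the SAP rule, and at most 3.4 under cut-off censoring.

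**The case against.** The strongest objection is that the premise is inferred. A reader might take the SAP to count every death up to the cut-off. It does not say that. SAP 5.3.3.1 speaks of patients not known to have died at the cut-off, and SAP 5.2.1 can be read as excluding late-arriving information of any kind. If deaths and contacts were both limited to what was known by the last contact, the bias would vanish (step 5, 0% row). This stands as a limit on the size. It does not remove the point, because the text expressly excludes the late proof of survival and nothing excludes the late-learned death.

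Second, the shift is modest against sampling error. With 183 per arm and uniform accrual, the Greenwood standard error at 24 months is about 4.3 points (avelumab) and 3.9 (PLD), so 2 points is about half a standard error. That is true, but the shift is systematic and avoidable.

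Third, 12-weekly calls do not apply to everyone. Scans, later therapies and adverse events also supply contact dates and narrow the gap to the 2-to-4-week range.

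Fourth, Table 8 affects only a label. That is correct. Its 13-week limit fits one call made a week late. With the ±7-day window two compliant calls can be 12 + 2 = 14 weeks apart, so a patient on schedule and later shown alive could still be listed as lost.

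**Conclusion.** The concern holds as a correctable bias in descriptive OS estimates. If all deaths dated up to the cut-off and known at lock are counted, the 24-month OS rate at a month-31 cut-off is about 2 to 4 points low in each arm. It is less if only some are captured, if contact is more frequent or if the cut-off falls later. Reverse Kaplan-Meier follow-up is understated as well, since it uses the same early censoring dates. These sizes rest on the assumed accrual shape, contact pattern and exponential survival.

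Two stronger conclusions are not supported. A reader might infer that the primary comparison is compromised, but the log-rank test, the hazard ratio and the 24-month arm difference barely change. A reader might also point to a large distortion at 30 months, but at month 31 almost nobody is at risk then, and that rate is barely estimable under either rule.

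**What to change.** In SAP 5.3.3.1, replace the sentence barring later dates with: *If any record available at database lock shows the patient alive after the cut-off date, or dead with a death date after it, OS is censored at the cut-off date; otherwise at the last contact on or before the cut-off.*

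Also:
- state that deaths dated on or before the cut-off and known at lock are events;
- exempt this use of vital status from SAP 5.2.1;
- apply Table 8 after this rule;
- align Protocol 9.3.1.1, which also censors at last contact.

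The SAP already reasons this way elsewhere: an adverse event ending after the cut-off is ongoing at the cut-off (5.3.2.2), and a patient still on treatment has the last dose set to the cut-off date (5.3.3.4).

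The cost is a few sentences and the cleaning of vital status between cut-off and lock. The documents give no lock interval. If it is under about 12 weeks, some survivors will have no later record and the correction may be only partial. Protocol section 9 records the final analysis as complete, so for that analysis the rule could serve only as a labelled supplementary run.
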